### 4.2 Intervention

Patients with cutaneous metastases from melanoma, Merkel cell carcinoma or other solid tumor malignancy will be screened for eligibility. If a patient is found to have anything other than cutaneous metastases from melanoma, Merkel cell carcinoma or other solid tumor malignancy, appropriate clinical management will be undertaken.

If eligible, patients will undergo baseline PET/CT imaging, quality of life assessment, followed by intralesional Talimogene Laherparepvec with or without radiotherapy.

Talimogene Laherparepvec will be administered at weeks 0, 3, 5, 7, 9, 11, 13 and 15. The first dose of Talimogene Laherparepvec will be  $10^6$  plaque forming units (PFU)/mL, followed three weeks later by a dose of  $10^8$  pfu/mL. Up to 4 mL will be injected at each treatment. Metastases will be injected, beginning with the largest tumor first, with volumes indicated below, until a maximum of 4 mL has been used.

Tumor size (longest dimension)	Talimogene Laherparepvec (TVEC) injection volume	Dose concentration
>5 cm	$\leq 4$ mL	$10^6$ PFU/mL at week 0, $10^8$ PFU/mL thereafter
2.6-5 cm	$\leq 2$ mL	$10^6$ PFU/mL at week 0, $10^8$ PFU/mL thereafter
1.6-2.5 cm	$\leq 1$ mL	$10^6$ PFU/mL at week 0, $10^8$ PFU/mL thereafter
0.6-1.5 cm	$\leq 0.5$ mL	$10^6$ PFU/mL at week 0, $10^8$ PFU/mL thereafter
$\leq 0.5$ cm	$\leq 0.1$ mL	$10^6$ PFU/mL at week 0, $10^8$ PFU/mL thereafter

Table 1. TALIMOGENE LAHERPAREPVEC injection volume and concentration based on tumor size.

Patients randomized to Arm A will receive 3 radiotherapy treatments (one treatment every 3-6 days) during weeks 3 and 4. The first treatment will occur 6 (+/- 2) hours after the Talimogene Laherparepvec administration at week 3.

Patients randomized to Arm B will receive Talimogene Laherparepvec alone, as described above, without radiotherapy.

Patients will undergo disease re-evaluation with PET/CT and quality of life assessment at week 16.

Patients with potential for clinical benefit may continue Talimogene Laherparepvec every 2 weeks, after week 15, for up to 24 weeks. This will be determined by the treating clinician.

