## **End of Treatment**

Week 16 ( $\pm$  1 week) or when TVEC is discontinued prior to week 15

- Physical examination
- ECOG performance status
- Vital signs (weight, heart rate, blood pressure, respiratory rate, oxygen saturation) will be assessed in clinic
- Adverse event review (including NCI PRO-CTCAE v1.0, Appendix C)
- Complete blood count (CBC)
- Comprehensive metabolic profile (CMP)
- Prothrombin and activated partial thromboplastin time test (PT&APTT)
- Research blood test (If TVEC stopped before week 15)
- Pregnancy test for women of childbearing potential (by either blood or urine)
- Research skin tumor biopsy (If TVEC stopped before week 15)
- Quality of life assessment (Skindex-16, Appendix B) to be completed by subjects
- Digital photography
- PET/CT (IV or oral contrast is not required, but is permissible if clinically indicated.)

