## **Follow-Up**

Week 20 ( $\pm$  1 week) or 4 weeks after last TVEC dose

- Adverse event review (including NCI PRO-CTCAE v1.0, Appendix C)

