## **12.0 CRITERIA FOR THERAPEUTIC RESPONSE/OUTCOME ASSESSMENT**

The primary endpoint for systemic efficacy is the week 16 response of the largest metastasis not injected with Talimogene Laherparepvec or irradiated. Overall subject level response is defined as partial or complete (>50% or greater decrease in largest lesion) by the modified World Health Organization (mWHO) criteria, and will include measurements of tumor size by CT component of PET/CT, by standard uptake value (SUV) by PET component of PET/CT, and clinically by digital photography. Please see Appendix A for complete radiographic assessment details and the mWHO response criteria.

Study radiologists will be specifically informed which lesion is the target for response assessment. A separate calculation of response within and outside the irradiated volume will be determined. Study radiologists will be blinded, however, as to which treatment arm the patient has been assigned.

Radiographic imaging evaluations are considered standard of care for patients treated for cutaneous metastases.

Patients are considered evaluable for the primary endpoint if they:

- Receive one dose of Talimogene Laherparepvec, and for patients enrolled on Arm A, one dose of RT, as well as a baseline and at least one post-baseline disease assessment
- Discontinue the study due to symptomatic progression, death, or toxicity at any point, even if they have not received one dose of Talimogene Laherparepvec and one dose of RT

Patients who discontinue the study and do not meet evaluable criteria above are replaceable. In this event, the replacement patient will be assigned to the same treatment arm that lost a patient.

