Note that in the above, all patients are assumed evaluable. However, it might happen that some patients are not evaluable due to various reasons such as withdrawal or loss to follow-up, etc. Such inevaluable patients will be replaced. We expect that about 13% of patients might need to be replaced. In other words, we expect to enroll up to 34 patients in total. The clinical efficacy of Talimogene Laherparepvec will be measured by the ORR and summarized by the sample proportion for each of the two arms. A comparison will be done between the two arms. Safety of Talimogene Laherparepvec will be summarized and compared similarly. QOL total and subscale scores will be summarized numerically and graphically, and trends will be observed and reported per arm. Wilcoxon rank sum tests will also be used to compare the QOL scores between the two arms for each assessment time point. DOR will be assessed using actuarial curves based on patients who achieved response and compared between the two arms using a stratified log-rank test. Time to response onset, progression free and overall survival will be analyzed in a similar way but will be based on all patients. Immunologic response data will be summarized descriptively, with mean, median and standard deviations calculated.

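### On the schedule in the protocol, response is read once after baseline, so the log-rank test of time to response onset cannot show earlier onset, and duration of response has no scheduled reading after week 16

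*Combined protocol and SAP*

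**What the plan says.** **Analysis.** Section 14.0 says of DOR: "DOR will be assessed using actuarial curves based on patients who achieved response and compared between the two arms using a stratified log-rank test". The next sentence carries the method over: "Time to response onset, progression free and overall survival will be analyzed in a similar way but will be based on all patients". Secondary objective 5 (Section 2.0) expects onset on T-VEC alone to resemble a published median of 4.1 months (range 1.2 to 16.9). It expects T-VEC with radiotherapy to be faster than that experience.

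**What counts as a response reading.** Section 12.0 lists "measurements of tumor size by CT component of PET/CT, by standard uptake value (SUV) by PET component of PET/CT, and clinically by digital photography". It continues: "Please see Appendix A for complete radiographic assessment details and the mWHO response criteria". Only the title of Appendix A is in the text available.

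**When readings are taken.** Section 8.0 requires PET/CT and photography at baseline. Section 4.2 says: "Patients will undergo disease re-evaluation with PET/CT and quality of life assessment at week 16". In Section 9.0 the End of Treatment visit is at week 16 (± 1), "or when TVEC is discontinued prior to week 15". The Section 10.0 table agrees. The one visit after that (week 20, or four weeks after the last dose) lists adverse event review and nothing else. Section 4.2 also allows extended treatment: "Patients with potential for clinical benefit may continue Talimogene Laherparepvec every 2 weeks, after week 15, for up to 24 weeks". No PET/CT or photography is attached to those doses.

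**What ends DOR and PFS.** Section 2.0 ends both at progression or death. Section 13.0 withdraws patients with clinically significant progression. Section 14.0 gives no censoring rule.

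**The concern.** A log-rank test uses the order in which events occur. If each patient is read once, at a time fixed by the calendar, the data say whether a response was present at that reading but not when it began. A time-to-response p-value would then be taken as evidence on speed when it carries essentially none, and objective 5 would appear to have been tested when it had not been.

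DOR has the mirror problem. A response first recorded at week 16 has no scheduled disease reading after it, so progression dates would come from assessments outside any stated schedule. PFS has its last scheduled mWHO reading at the same visit.

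**Working it through.** **1. Readings on the schedule (Sections 8.0, 9.0 and 10.0).**

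| Item | Baseline | Treatment visits | Week 16 or early End of Treatment | Later |
|---|---|---|---|---|
| PET/CT (size, SUV) | yes | none | yes | none |
| Digital photography | yes | none | yes | none |
| Physical examination | yes | weeks 0, 3, 5, 7, 11, 15 | yes | none |
| Adverse event review | no | each injection visit | yes | yes |

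Stopping T-VEC early moves the one reading forward and does not add a second. Two-weekly extension doses would run to week 23 or to week 39, depending on how the 24 weeks are counted. No disease reading is scheduled under either count.

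**2. The plan's own figures.** Section 14.0 gives none for the log-rank tests. Its Simon design reproduces: early stopping is 0.925^9 = 0.496 (stated 0.50) and 0.73^9 = 0.059 (stated 0.06), with type I error 0.094 and power 0.802. This confirms 15 evaluable patients per arm as the basis for what follows.

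**3. Log-rank with every reading dated week 16.** In a stratum of n patients, with n1 in Arm A, d responders in all and O responders in Arm A:

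- E = d·n1/n
- V = d·(n1/n)·(1 − n1/n)·(n − d)/(n − 1)
- statistic = [Σ(O − E)]² / ΣV

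This is the Cochran-Mantel-Haenszel statistic for week-16 response.

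- Unstratified, 8/15 against 4/15: O − E = 8 − 6 = 2; V = 12 × 0.5 × 0.5 × 18/29 = 1.862; statistic = 4/1.862 = 2.148 (p = 0.143).
- Pearson chi-square on the same data: (4/15)² / (0.4 × 0.6 × 2/15) = 2.222 (p = 0.136), and 2.222 × 29/30 = 2.148.
- Illustrative three-stratum split (4/7 v 2/7, 2/4 v 1/4, 2/4 v 1/4): Σ(O − E) = 1 + 0.5 + 0.5 = 2; ΣV = 0.923 + 0.536 + 0.536 = 1.995; statistic = 2.006 (p = 0.157), identical to Cochran-Mantel-Haenszel.
- In 4,000 simulated trials of 15 per arm, the two stratified statistics never differed by more than 9e-16.

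**4. Equal week-16 rates, different onset.** Suppose radiotherapy moved every response from week 12 to week 6 and left 6/15 responding in each arm. Dated to week 16, O − E = 6 − 6 = 0 and the statistic is exactly 0.

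A simulation points the same way. It assumed 40% response in both arms, with onset uniform over weeks 2–6 in Arm A and 10–16 in Arm B, tested at two-sided 0.05. The rejection rate was 4.5% with one week-16 reading, 8.0% with four-weekly readings and 8.2% with continuous observation.

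**5. Spread of visit dates.** With dates uniform over weeks 15–17 (simulated at an assumed 45% v 26.4%), the correlation with the week-16 result falls to 0.70. The difference comes from appointment dates.

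**6. The published onset figure.** 4.1 months × 30.44/7 = 17.8 weeks, which is after the only reading. Section 3.0 gives the median as 16 weeks.

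**7. DOR.**

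- Expected responders: 26.4% in both arms gives 2 × 15 × 0.264 = 7.9; 26.4% against an assumed 45% gives 15 × (0.264 + 0.45) = 10.7. That is about 8 to 11 in total.
- Power for an assumed hazard ratio of 0.5, if every responder has an event, is Φ(ln 2 × √d/2 − z).
- At two-sided 0.05 (z = 1.96): d = 8 gives Φ(0.980 − 1.960) = 0.16; d = 11 gives Φ(1.149 − 1.960) = 0.21.
- No level is stated for secondary tests. At two-sided 0.10 (z = 1.645) the values are 0.25 and 0.31.

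**The case against.** **Appendix A may add assessments.** Section 12.0 refers to it for the full radiographic details, and its evaluability rule speaks of at least one post-baseline assessment, which allows more than one. This stands as a limit: the point applies to the schedule in the body of the protocol. A reader might infer that the trial has only one assessment under any document, and the text available does not establish that.

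**Lesions are sized at every injection.** Section 4.2 sets injection volume and order by lesion size, and physical examinations fall at six treatment visits. So information on timing will exist for injected lesions. But nothing in the plan makes those sizes mWHO readings or dates a response from them, and uninjected disease is not covered.

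**The time-to-response test does not simply repeat the planned response comparison.** A reader might infer that it does. Equality is exact only when all readings carry the same date, and then it is with the stratified form. The response-rate comparison described for the primary endpoint is an unstratified two-sample proportion test on one uninjected, unirradiated lesion. The nearest match is the secondary ORR comparison. With assumed strata of 60/20/20%, the stratified log-rank and the unstratified proportion z correlate at 0.965.

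**DOR is not empty.** Deaths count, and Sections 11.1.4 and 13.0 both act on progression, so events will occur. Nor is 4.0 (15 × 0.264) a ceiling on responders per arm. It is an expected value: the chance of 5 or more of 15 is 0.36, and the protocol expects a higher rate with radiotherapy.

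**Low power is admitted.** Section 14.0 concedes it for the response-rate comparison, and it is normal for secondary tests at this size. It is not the defect here. More patients would not cure the time-to-response problem, because onset is not observed.

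**Follow-up is implied.** Section 1.0 foresees enrolment over 2–3 years in a study of 3–4 years, and imaging is called standard of care. That makes later data obtainable, but it does not say which data are collected or where they are cut off.

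**Conclusion.** The point holds on the schedule in the body of the protocol. The stratified log-rank test of time to response onset carries essentially no information about onset and cannot address objective 5. It equals the Cochran-Mantel-Haenszel test of week-16 response when all readings are dated week 16. Spread within weeks 15–17 reflects appointments. This assumes that Appendix A schedules nothing further and that response is dated from the Section 12.0 measures.

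For DOR the conclusion is narrower. Progression after a week-16 response would be dated from unscheduled assessments, in about 8 to 11 responders, with power of about 0.16 to 0.21 at a hazard ratio of 0.5 and two-sided 0.05 even if all have events. That supports descriptive reporting, not a claim that DOR cannot be estimated. The unstated censoring rules for PFS and OS are missing detail to be supplied and do not carry the point.

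It should be fixed. A reader might infer that the main result is undermined, but the primary endpoint is itself a week-16 response, so it, the Simon rule and the choice between arms are unaffected.

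**What to change.** - **Time to response (Sections 2.0 and 14.0).** Drop the between-arm log-rank test and the statement about earlier onset. If timing is to be kept, record the lesion sizes already needed at injection visits as dated response readings, and say that they cover injected lesions only. Power would stay low.
- **DOR (Section 14.0).** Report it descriptively, without a between-arm test.
- **Progression and survival (Sections 9.0, 10.0 and 13.0).** State that progression and vital status after week 16, and after withdrawal, are abstracted from standard-of-care records to a stated cut-off. Add censoring rules, for example PFS at the last disease assessment and OS at the date last known alive. Otherwise report the proportion progression-free at week 16, and OS descriptively.
- **Appendix A.** If it schedules further assessments, cite them in Sections 10.0 and 14.0.

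The cost is the loss of the between-arm timing and DOR tests, plus modest record abstraction for up to 34 patients at one centre. The changes to the tests are wording only.

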**Secondary Objectives:**

1. To assess the clinical efficacy of Talimogene Laherparepvec with or without radiotherapy in patients with cutaneous metastases from melanoma, Merkel cell carcinoma, or other solid tumor malignancy. Clinical efficacy will be measured by determining the objective response rate (ORR) defined as patients achieving complete response or partial response defined by the modified World Health Organization (mWHO) criteria. Response will be assessed approximately 16 weeks after the first treatment. Among patients randomized to receive Talimogene Laherparepvec, we expect ORRs to be comparable to previous studies (26.4% 95% CI 21.4-31.5%). Patients randomized to receive Talimogene Laherparepvec and radiotherapy are expected to have ORRs higher than previously published studies of Talimogene Laherparepvec alone.
2. To assess the safety of Talimogene Laherparepvec with or without radiotherapy in patients with cutaneous metastases from melanoma, Merkel cell carcinoma, or other solid tumor malignancy as measured by the frequency of adverse events (grade 2-5 adverse events). The window for adverse event assessment will include the 20 week time period from first treatment until 5 weeks after last treatment. We expect that frequency and grade of adverse events in patients receiving Talimogene Laherparepvec will be similar to previous studies of Talimogene Laherparepvec alone, and that radiotherapy will increase the frequency and grade of adverse events.
3. To evaluate the patient reported quality of life following Talimogene Laherparepvec with or without radiotherapy in patients with cutaneous metastases from melanoma, Merkel cell carcinoma, or other solid tumor malignancies treated with Talimogene Laherparepvec with or without hypofractionated radiotherapy. It is expected that quality of life (described further in section 12.0) will improve after Talimogene Laherparepvec with or without radiotherapy.
4. To assess the duration of response (DOR) in patients achieving a partial or complete response. DOR will be defined as the duration of time from occurrence of partial or complete response until first occurrence of progression or date of death if the patient dies due to any causes before progression.

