5. To assess the time to response onset in following Talimogene Laherparepvec with or without radiotherapy. It is expected that the time to response onset in patients randomized to receive Talimogene Laherparepvec will be similar to previous studies of Talimogene Laherparepvec alone (median 4.1 months, range 1.2-16.9 months). It is anticipated that the time to response onset in patients receiving Talimogene Laherparepvec and radiotherapy will be earlier than prior studies of Talimogene Laherparepvec alone.

6. To estimate progression free and overall survival in patients receiving Talimogene Laherparepvec with or without radiotherapy for cutaneous metastases from melanoma and Merkel cell carcinoma. Progression free survival will be defined as the time elapsed from start of protocol treatment until progression (according to mWHO criteria) or death.

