## **13.0 CRITERIA FOR REMOVAL FROM STUDY**

Consent for participation in the study may be withdrawn by the patient or patient's health care proxy at any time.

If at any time, the patient develops clinically significant progressive disease, s/he will be withdrawn from the study and referred for alternative therapy.

If at any time the patient is found to be ineligible for the protocol as designated in the section on Criteria for Subject Eligibility (i.e., a change in diagnosis), the patient will be removed from the study.

If at any time, the protocol therapy jeopardizes the safety of the patient, s/he may be withdrawn from the study.

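### Time to response onset: an actuarial curve in all patients, with no stated rule for death or withdrawal for progression, would by default overstate the share of patients who respond

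*Combined protocol and SAP*

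**What the plan says.** Section 14.0 first fixes the method for duration of response (DOR): "DOR will be assessed using actuarial curves based on patients who achieved response and compared between the two arms using a stratified log-rank test". The next sentence extends it: "Time to response onset, progression free and overall survival will be analyzed in a similar way but will be based on all patients".

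For DOR, death is part of the endpoint; Section 2.0, secondary objective 4, ends it at "first occurrence of progression or date of death if the patient dies due to any causes before progression". Progression free survival (PFS, secondary objective 6) likewise runs "until progression (according to mWHO criteria) or death". Time to response has no such definition. Secondary objective 5 only names it, "To assess the time to response onset in following Talimogene Laherparepvec with or without radiotherapy", and sets it against a prior median of 4.1 months (range 1.2 to 16.9). No section gives its censoring rule or names competing events.

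Section 13.0 makes early loss of observation part of the design: "If at any time, the patient develops clinically significant progressive disease, s/he will be withdrawn from the study and referred for alternative therapy".

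**The concern.** The shared method suits PFS and overall survival, where death is an event. Time to response has a different structure. A patient who dies, or is withdrawn for progression, without having responded will not be seen to respond later. These are competing events.

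A one-event actuarial curve handled in the ordinary way takes such patients out of the risk set when they leave. In effect it assumes that they would have gone on to respond at the rate of those who remain. One minus the curve then estimates response in a hypothetical setting without deaths or withdrawals, and not the share of enrolled patients who respond.

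Two displays from the same patients would therefore disagree. The ORR is a sample proportion per arm. Section 12.0 also keeps patients who discontinue for symptomatic progression, death or toxicity evaluable for the primary endpoint. The response curve would drop those same patients. A reader could take the higher figure from the curve as the response probability, or read a median from it and compare that with 4.1 months.

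**Working it through.** **The plan's own figures.** Section 14.0 gives no figure for time to response. The stopping probabilities it states for the two-stage design do reproduce: 0.925^9 = 0.496 (stated 0.50) and 0.73^9 = 0.059 (stated 0.06). They concern the primary endpoint and do not depend on this point.

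**Inputs.**
- Share responding by week 16: 27% (the promising rate in Section 14.0). As a second value, 26.4% (the expected ORR for the drug alone, Section 2.0).
- Patients per arm: 15 (Section 14.0).
- Share lost to death or withdrawal for progression before response, by week 16: not in the documents. Assumed 10% to 50%.

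**Step 1: what the curve reads for a given true share.** Let p be the true share responding by week 16 and q the share lost first, with constant cause-specific hazards. The total cumulative hazard is H = −ln(1 − p − q). The response part is L = H·p/(p + q). With losses censored, the curve reads 1 − exp(−L). Cumulative incidence reads p. For p = 27%:

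| Lost first, q (assumed) | H | L | Curve reads | Excess over 27% (points) |
|---|---|---|---|---|
| 10% | 0.462 | 0.337 | 28.6% | 1.6 |
| 20% | 0.635 | 0.365 | 30.6% | 3.6 |
| 30% | 0.844 | 0.400 | 33.0% | 6.0 |
| 40% | 1.109 | 0.447 | 36.0% | 9.0 |
| 50% | 1.470 | 0.515 | 40.3% | 13.3 |

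For p = 26.4% and q = 30% the curve reads 32.2%, an excess of 5.8 points. The excess also rises with the response rate. At q = 30% it is 4.2 points for a true 20% and 8.2 points for a true 35%.

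**Step 2: two arms with the same share responding.** Suppose 4 of 15 respond in each arm, all read at week 16, and losses before then are 2 in one arm and 5 in the other (assumed). The curve is responders/(15 − earlier losses):
- 2 losses: 4/13 = 30.8%
- 5 losses: 4/10 = 40.0%
- Cumulative incidence in both arms: 4/15 = 26.7%

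The curves differ by about 9 points, with the higher one in the arm that lost more patients, although the same share responded.

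**Step 3: two arms with the same response hazard.** Let the response hazard be such that 27% would respond by week 16 with no loss: L = −ln(0.73) = 0.315. Let the competing hazard alone remove m, so M = −ln(1 − m). The true share responding is L/(L + M) × (1 − exp(−(L + M))). For m = 10%, 20%, 30%, 40% and 50% this gives 25.7%, 24.3%, 22.9%, 21.4% and 19.8%. The actuarial curve reads 27% every time. Here the curves agree between arms whatever the losses, and it is the true shares that differ. The overstatement still grows with losses, from 1.3 to 7.2 points.

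**Step 4: the median.** With an ORR near 26.4%, the share responding does not reach one half, so no median exists among all patients. Censoring can produce one: 4 responders with 7 of 15 lost earlier (assumed) gives 4/(15 − 7) = 50% at week 16.

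**The case against.** The best reply is that the plan does not say that these patients are censored. It says only that the method is similar and the population is all patients. Keeping patients who fail early at risk as non-responders would also be an actuarial curve in all patients, and it would not be inflated. This stands as a limit on the wording: a reader might infer that Section 14.0 prescribes censoring at death and progression, and it does not. It does not remove the point. Censoring is the ordinary default, nothing overrides it, and following the stated method in its usual form gives a biased curve.

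A reader might also infer that unequal losses by themselves create a false difference between arms. Step 3 shows that this is not general. With equal response hazards the curves agree. The gap in Step 2 arises because the shares responding are equal, so the response rate among those still at risk differs. Nor is the log-rank test invalid: it compares cause-specific response hazards, but not the share responding.

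The consequences are limited too. In the Step 2 example the exact 95% interval for 4/15 is about 8% to 55%, and a log-rank test at the single jump gives p of about 0.65, so no inference would turn on it. Time to response is a secondary endpoint with no decision rule, and the ORR will stand beside the curve.

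Finally, cumulative incidence cannot be compared with the prior median of 4.1 months, which at an ORR of 26.4% can only describe responders. PET/CT after baseline is scheduled only at week 16 or at early discontinuation (Sections 9.0 and 10.0), so any curve says little about timing. This stands, and is why the fix includes a summary among responders.

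**Conclusion.** The point holds for the response curve and for percentages or medians read from it. The upward direction follows whenever patients are lost before response and are censored. The size rests on a loss rate that the documents do not give and, in Step 1, on constant hazards: about 2 to 13 points over the assumed range of 10% to 50%. Curves may differ between arms when the shares responding do not, but need not.

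It would be wrong to carry this to the main conclusions. The two-stage decision and the choice of arm rest on response proportions, and the ORR is a proportion as well. The change should still be made, because the method as written does not estimate what readers will take the curve to show.

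**What to change.** In Section 14.0, take time to response out of the sentence it shares with PFS and overall survival, and state:

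- The event is the first partial or complete response by the modified WHO criteria. Death and withdrawal for progression without prior response are competing events.
- The estimate is the cumulative incidence of response per arm in all patients. If the arms are compared, use Gray's test stratified by disease type. Equivalently, such patients may be kept at risk as non-responders to the end of assessment.
- For comparison with the prior median of 4.1 months, time to response is summarised descriptively among responders (median and range), beside the ORR.

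PFS, overall survival and DOR keep their present method. The cost is a few sentences and standard software, with no new patients or data. The downside is that the response curve will look less favourable than the actuarial one.
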